### **8.2.9 Proportion of subjects who achieved “seizure-free” status for subjects who completed the Maintenance Period**

A subject who completed the Maintenance Period will be defined as seizure-free if the subject did not report any seizures during the Maintenance Period, that is, there are no diary records during the Maintenance Period with either a count >0 or a reported seizure code with an unknown or missing seizure count.

Days with missing seizure diary data will be excluded from the determination of seizure free status as long as the percentage of days in the Maintenance Period with missing seizure diary data does not exceed 20%.

The number and percentage of subjects who achieved seizure free status during the Maintenance Period will be presented by treatment group.

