4.1.2 Secondary efficacy variables

The secondary efficacy variables are described below:

- Proportion of responders, where a responder is a subject experiencing a 50% or greater reduction in partial-onset seizure frequency from Baseline to the Maintenance Period
- Proportion of subjects experiencing a $\geq 25\%$ to $< 50\%$, 50% to 75%, or $> 75\%$ reduction in partial-onset seizure frequency from Baseline to the end of Maintenance Period
- Change in partial-onset seizure frequency per 28 days from Baseline to the entire treatment (ie, Titration+Maintenance Periods)
- Proportion of subjects experiencing a $\geq 25\%$ to $< 50\%$, 50% to 75%, or $> 75\%$ reduction in partial-onset seizure frequency from Baseline to the entire treatment (ie, Titration+Maintenance Periods)
- Proportion of subjects experiencing no change in partial-onset seizure frequency (between $< 25\%$ reduction and $< 25\%$ increase) from Baseline to the entire treatment (ie, Titration+Maintenance Periods)
- Proportion of subjects experiencing an increase in partial-onset seizure frequency of $\geq 25\%$ from Baseline to the entire treatment (ie, Titration+Maintenance Periods)
- Change in partial-onset seizure frequency per 28 days from Baseline to the entire treatment (ie, Titration+Maintenance Periods) by seizure type
- Proportion of seizure-free days during the Maintenance Period for subjects who entered the Maintenance Period

- Proportion of subjects who achieved “seizure-free” status (yes/no) for subjects who completed the Maintenance Period

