For subjects who enter the Maintenance Period, proportion of seizure-free days during the Maintenance Period will be calculated and summarized by treatment group descriptively.

For subjects who complete the Maintenance Period, the number and percentage of subjects who achieved "seizure-free" status during the Maintenance Period will be tabulated and presented by treatment group descriptively.

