### 2.3 Study design and conduct

This is a Phase 3, multicenter, double-blind, randomized, placebo-controlled, parallel-group study to evaluate the efficacy and safety of LCM (LCM 8mg/kg/day to 12mg/kg/day [oral solution] for subjects weighing <30kg, LCM 6mg/kg/day to 8mg/kg/day [oral solution] for subjects weighing  $\geq$ 30kg to <50kg, and LCM 300mg/day to 400mg/day [tablets] for subjects weighing  $\geq$ 50kg, or matching placebo) as adjunctive therapy in subjects with epilepsy  $\geq$ 4 years to <17 years of age with uncontrolled partial-onset seizures. Subjects weighing  $\geq$ 50kg who are unable or unwilling to swallow tablets may receive LCM oral solution. However, they are not permitted to exceed the maximum dose of LCM 400mg/day.

A total of approximately 300 subjects are planned to be randomized at approximately 155 sites. The study will be conducted in the [REDACTED] region with the possibility to expand the study to other countries and regions if deemed necessary.

Stratification of subjects by age category is planned to ensure that an appropriate number of subjects will be included in each age range. The age categories are as follows:

- At least 100 subjects  $\geq$ 4 years to <12 years of age
- At least 100 subjects  $\geq$ 12 years to <17 years of age

Subjects with uncontrolled partial-onset seizures will be enrolled into an 8-week Baseline Period. At the end of the Baseline Period (Visit 2), eligible subjects will be randomized in a double-blind manner to 1 of 2 parallel treatment arms: LCM or placebo in a 1:1 ratio. At the end of Visit 2, subjects should take the first dose of study medication while in the clinic. At each subsequent clinic visit, subjects should take study medication (and any concomitant AEDs) at the regular times. Study medication will be administered orally bid at approximately 12-hour intervals in the morning and in the evening.

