## 3 DATA ANALYSIS CONSIDERATIONS

### 3.1 General presentation of summaries and analyses

Statistical analysis and generation of tables, figures, subject data listings, and statistical output will be performed using SAS Version 9.3. All tables and listings will use Courier New font size 9.

Descriptive statistics will be displayed to provide an overview of the study results. For categorical parameters, the number and percentage of subjects in each category will be presented. The denominator for percentages will be based on the number of subjects appropriate for the purpose of analysis. Unless otherwise noted, all percentages will be displayed to 1 decimal place. No percentage will be displayed for zero counts, and no decimal will be presented when the percentage is 100%. For continuous parameters, descriptive statistics will include number of subjects (n), mean, standard deviation (SD), median, minimum, and maximum.

Decimal places for descriptive statistics will always apply the following rules:

- “n” will be an integer.
- Mean, SD, and median will use 1 additional decimal place compared to the original data.
- Coefficient of variance (CV[%]) will be presented with 1 decimal place.
- Minimum and maximum will have the same number of decimal places as the original value.

Statistical tests of efficacy variables will be presented as 2-sided p-values rounded to 4 decimal places. P-values less than 0.0001 will be presented as “<0.0001” and p-values greater than 0.9999 will be presented as “>0.9999.” Statistical comparison will be performed at the 0.0500 level of significance.

A complete set of data listings containing all documented data and all calculated data (eg, change from Baseline) will be generated, and will be sorted by site, subject number and visit (where applicable).

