## **8.2 Statistical analysis of the secondary efficacy variables**

The secondary efficacy variables will be summarized and/or analyzed for the FAS.

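### Seizure-free status is reported only among Maintenance completers, so the percentages by arm do not compare randomised groups

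*SAP*

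**What the plan says.** Protocol 4.1.2 lists seizure-free status as a secondary efficacy variable "for subjects who completed the Maintenance Period". Protocol 9.1 and SAP 2.2.1.2 repeat the restriction. Protocol 13.3.2 sets the presentation: "For subjects who complete the Maintenance Period, the number and percentage of subjects who achieved" seizure-free status, by treatment group and descriptively.

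The title of SAP 8.2.9 carries the same limit ("status for subjects who completed the Maintenance Period"), and its definition begins "A subject who completed the Maintenance Period will be defined as seizure-free if the subject did not report any seizures during the Maintenance Period". The output is then described without a denominator: "The number and percentage of subjects who achieved seizure free status during the Maintenance Period will be presented by treatment group". Two general rules leave room for doubt. SAP 8.2 says "The secondary efficacy variables will be summarized and/or analyzed for the FAS", and SAP 3.1 says "The denominator for percentages will be based on the number of subjects appropriate for the purpose of analysis". Neither document describes a version in all FAS subjects, and neither has a rule that counts non-completers as not seizure-free.

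Other secondary variables treat early leavers differently. SAP 4.2.1 keeps them in the seizure-frequency analyses by carry-forward, and SAP 8.2.2 classes any subject without a 50% reduction as a non-responder. SAP 8.2.8 calculates seizure-free days for everyone who enters Maintenance.

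**The concern.** Randomisation is "LCM or placebo in a 1:1 ratio", and it protects a comparison only while the groups compared are those randomised. Completing Maintenance happens later, and both treatment and outcome can influence it.

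- **Tolerability.** Protocol 6.3 requires withdrawal for intolerable adverse events. Protocol 7.2.1 and 7.2.2 withdraw subjects who cannot reach the minimum target dose or who need a dose change in Maintenance.
- **Outcome.** Protocol 6.3 also requires withdrawal for convulsive status epilepticus, for rescue medication beyond the permitted amount, and for any alteration in the daily dose of a concomitant AED. Subjects who leave for these reasons are unlikely to have been seizure-free.

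Both routes take subjects out of the denominator. At stake is how two percentages printed side by side will be read. Seizure-free status looks like the top of the response scale whose next step, more than 75% reduction (SAP 8.2.3), includes early leavers. The two would stand on different denominators.

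**Working it through.** **The plan's own figures.** The documents state no expected seizure-free rate and no dropout by arm, so there is no figure for this endpoint to reproduce. The sample size does reproduce: 2 × (1.960 + 0.842)² × 0.73² / 0.249² rounds up to 135 per arm. The enrolled number, 154 per arm, is 135 × 1.14; dividing instead, 135 / (1 − 0.14), gives 157. I use 154 as the arm size below.

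**Formula.** For one arm, let q be the seizure-free share of all randomised subjects, d the share not completing Maintenance, and r the seizure-free rate among non-completers. Then

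completers' rate = (q − d × r) / (1 − d).

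If non-completers count as not seizure-free, r = 0 and the rate is q / (1 − d). Relative to all randomised subjects, this raises an arm's figure by 1/0.86 = 1.16 at 14% dropout and by 1/0.76 = 1.32 at 24%.

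**Inputs.** The 14% and 24% are overall study dropout rates from SAP 2.4 and 2.4.1, used here as a stand-in for non-completion of Maintenance. The splits between arms and the values of q are assumptions. Each split averages 14%. The arms are called A and B because the documents do not say which would lose more.

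**Equal q in both arms, r = 0** (A vs B in %, gap in points from unrounded values):

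| Dropout A vs B | q = 5% | q = 10% | q = 15% | Ratio A/B |
|---|---|---|---|---|
| 14% vs 14% | 5.8 vs 5.8, gap 0 | 11.6 vs 11.6, gap 0 | 17.4 vs 17.4, gap 0 | 1.00 |
| 19% vs 9% | 6.2 vs 5.5, gap 0.7 | 12.3 vs 11.0, gap 1.4 | 18.5 vs 16.5, gap 2.0 | 1.12 |
| 24% vs 4% | 6.6 vs 5.2, gap 1.4 | 13.2 vs 10.4, gap 2.7 | 19.7 vs 15.6, gap 4.1 | 1.26 |

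With all randomised subjects in the denominator, every gap is 0. Swapping the dropout rates reverses each sign.

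**In whole subjects.** Take 154 per arm, 15 seizure-free in each, and dropout of 24% vs 4%. Completers number 154 × 0.76 = 117 and 154 × 0.96 = 148. The completers' rates are 15/117 = 12.8% and 15/148 = 10.1%; over all randomised, both are 15/154 = 9.7%. The standard error of the completers' difference is √(0.128 × 0.872/117 + 0.101 × 0.899/148) = 0.040. The 2.7-point gap is therefore about two thirds of one standard error.

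**Dependence on r** (q = 10%, dropout 24% vs 4%):

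- r = 0: gap +2.7 points
- r = 5%: gap +1.4 points
- r = 10%: gap 0
- r = 15%: gap −1.4 points

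So the arm with more dropout gains only when dropouts are less likely to be seizure-free than completers.

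**The case against.** The plan has a fair defence. The restriction is in the variable's own name, is pre-specified, and agrees between protocol and SAP. No test is planned, so no p-value depends on it. The primary ANCOVA and the 50% responder model are run in the FAS with early leavers retained. SAP 8.2.9 reports the number as well as the percentage, and SAP 5.1 gives disposition by arm for the FAS, so a reader could work out the FAS percentage. Requiring completion is also coherent: freedom from seizures over ten weeks cannot be observed in someone who leaves in week two. Counting leavers as failures asks a different question, one that mixes tolerability with seizure control.

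Most of this stands, and it limits the weight of the point. It does not make the completers' percentages a randomised comparison, and the absence of a test does not stop readers from comparing two percentages.

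A reader might also infer that the choice favours LCM. Protocol section 2 reports dose-related adverse events in adults, which makes more tolerability withdrawals on LCM plausible. But the seizure-linked withdrawals could fall more on placebo, and neither document gives dropout by arm. That inference is not supported.

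**Conclusion.** The point holds in a limited form. The reported percentages are conditional on a post-randomisation event. They can differ between arms when equal shares of randomised subjects become seizure-free. The arm with more dropout shows the higher figure if dropouts are less likely to be seizure-free than completers, which the withdrawal criteria make plausible.

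The 0.7 to 4.1 point range rests on assumed dropout splits and seizure-free shares, and on non-completers counting as not seizure-free. It illustrates possible size and predicts no direction. Nothing here touches the primary analysis, its significance level or its power.

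Separately, SAP 8.2.9 should state its denominator. The section title and Protocol 13.3.2 point to completers, while SAP 8.2 names the FAS. This is a gap in wording. It does not show that the two documents conflict on the endpoint.

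**What to change.** In SAP 8.2.9:

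- State the denominator of the completers' percentage, and say how a completer with more than 20% missing diary days is classed, which the section leaves open.
- Add a row with all FAS subjects in the denominator and non-completers counted as not seizure-free.
- Show it beside the protocol-defined completers row, with the number of completers in each arm.
- Record the addition in SAP 3.9, which now reports no changes to the protocol's analyses.

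Which row is called the main one is a matter of preference; what matters is that both appear.

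The cost is a few lines of SAP text and one table row, with no new data. The added percentage will be lower than the completers' figure in any arm with dropout, and it is a composite that also reflects tolerability. Because the FAS requires post-Baseline seizure data (SAP 3.5.2), the added row is close to an as-randomised comparison but not exactly one.

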## **8.3 Analysis of other efficacy variables**

The following efficacy variables will be summarized for the FAS.

### **8.3.1 Clinical Global Impression of Change**

The Clinical Global Impression of Change is a 7-point categorical rating scale in which the investigator assesses the subject’s change from Baseline in clinical status, including an evaluation of seizure frequency and intensity, the occurrence of AEs, and a subject’s functional status. This will be assessed at Visit 8, or at ETV in case of early termination.

The number and percentage of subjects by Clinical Global Impression of Change value will be summarized for Visit 8 and Last Visit by treatment group. The denominator for the percentage calculation will be based on the number of subjects with non-missing values. In addition, the 3 improvement values (Very much improved, Much improved, and Minimally improved) grouped as “Improved” and the 3 worsening values (Minimally worse, Much worse, and Very much worse) grouped as “Worsened”, together with the “No change” group will be summarized for Visit 8 and Last Visit by treatment group. The denominator for the percentage calculation will be based on the number of subjects with non-missing values.

Clinical Global Impression of Change data will be listed.

### **8.3.2 Caregiver’s Global Impression of Change**

The Caregiver’s Global Impression of Change is a 7-point categorical rating scale in which the caregiver assesses the subject’s change from Baseline in clinical status, including an evaluation of seizure frequency and intensity, the occurrence of AEs, and a subject’s functional status. This will be assessed at Visit 8, or at ETV in case of early termination.

The number and percentage of subjects by Caregiver’s Global Impression of Change value will be summarized for Visit 8 and Last Visit by treatment group. The denominator for the percentage calculation will be based on the number of subjects with non-missing values. In addition, the 3 improvement values (Very much improved, Much improved, and Minimally improved) grouped as “Improved” and the 3 worsening values (Minimally worse, Much worse, and Very much worse) grouped as “Worsened”, together with the “No change” group will be summarized for Visit 8 and Last Visit by treatment group. The denominator for the percentage calculation will be based on the number of subjects with non-missing values.

Caregiver’s Global Impression of Change data will be listed.

### **8.3.3 PedsQL assessment**

The PedsQL is a validated instrument that consists of generic core scales suitable for use with pediatric populations, including those with acute or chronic health conditions. The PedsQL will be administered only in countries where a translated version is available and will be completed at Visit 2 (Baseline), Visit 8, and at ETV in case of early termination.

PedsQL generic core scale scores will be calculated for each of the following 4 PedsQL scales: Physical Functioning, Emotional Functioning, Social Functioning, and School Functioning. The PedsQL assessment is retrospective to the prior 4 weeks, and individual items are scored using a 5-point Likert scale (0 to 4 representing responses of: never, almost never, sometimes, often, or almost always). These scores of 0 to 4 will be transformed by the function:  $100 - (\text{response} \times 25)$  in order to generate scores of 0, 25, 50, 75, and 100 where a higher value represents a better HRQoL.

Each scale score is then calculated as the mean of the non-missing categorized items if 50% or more of the items are non-missing.

The above algorithm will also be used to calculate an overall Total Scale Score (all scales) and the Psychosocial Health Summary Score (a combination of the emotional, social and school functioning questions) for each subject.

Calculated values and change from Baseline for the total scale score, psychosocial health score and each of the 4 scale scores will be summarized for each visit and Last Visit by treatment group. Subgroup summaries by age will be performed using the age groupings for which different questionnaires were entered:  $\geq 2$  to  $\leq 4$  years,  $\geq 5$  to  $\leq 7$  years,  $\geq 8$  to  $\leq 12$  years, and  $\geq 13$  to  $\leq 18$  years.

All PedsQL data will be listed.

#### **8.3.4 Concomitant medical procedures**

Subjects who had any concomitant medical procedures during the course of the study based on the Concomitant Medical Procedures eCRF will be listed. These will be attributed to the study periods based on the date of the procedure as defined in section 3.2.2. Additionally, subjects who had any procedures or surgeries prior to study entry based on the Procedure History eCRF will also be listed.

The number of concomitant medical procedures per subject will be summarized by treatment group for the Baseline Period and the entire Treatment Period, separately. The number of concomitant medical procedures per subject will be summarized using the categories 0, 1, 2, and 3 or more.

#### **8.3.5 Healthcare provider consultations**

Healthcare provider consultations not foreseen by the protocol will be attributed to study periods as defined in section 3.2.2 based on the date of consultation.

The number of healthcare provider consultations per subject during the Baseline Period and during the entire Treatment Period will be summarized, separately, by treatment group. The number of healthcare provider consultations will be summarized using the categories 0, 1, 2, 3, 4, and 5 or more.

The number of healthcare provider consultations during the Baseline Period and during the Treatment Period, separately, will be summarized by type of provider (General Practitioner, Specialist Physician, Nurse, or Other) and treatment group. Percentages will be relative to the number of healthcare provider consultations during the Baseline Period and during the entire Treatment Period, respectively.

All healthcare provider consultations data will be listed.

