1 SUMMARY

SP0969 is a Phase 3, multicenter, double-blind, randomized, placebo-controlled, parallel-group study to evaluate the efficacy and safety of lacosamide (LCM) as adjunctive therapy in subjects with epilepsy ≥ 4 years to < 17 years of age with partial-onset seizures.

A total of approximately 300 subjects with uncontrolled partial-onset seizures will be enrolled at approximately 149 sites in [REDACTED] and other regions as deemed necessary. The maximum duration of a subject's study participation is up to 36 weeks. The maximum duration of study medication administration is 24 weeks.

The study is comprised of the following: an 8-week Baseline Period; a 6-week Titration Period (with study medication dosing flexibility allowed based on tolerability) to achieve a target dose for the Maintenance Period (LCM 8mg/kg/day to 12mg/kg/day for subjects weighing < 30 kg, LCM 6mg/kg/day to 8mg/kg/day for subjects weighing ≥ 30 kg to < 50 kg, and LCM 300mg/day to 400mg/day for subjects weighing ≥ 50 kg, or matching placebo); a 10-week Maintenance Period at the dose of study medication achieved on the final day of the Titration Period; and then a 4-week blinded Transition Period (for subjects who plan to enter the open-label extension study [EP0034]) or a blinded Taper Period (2 to 4 weeks) followed by a 30-day Safety Follow-Up Period (for subjects who will not be entering EP0034).

The assessment of efficacy is based on partial-onset seizure frequency. The primary efficacy variable is the change in partial-onset seizure frequency per 28 days from Baseline to the Maintenance Period. Secondary and other efficacy variables will allow further exploration of the effect of LCM on partial-onset seizure frequency, global impressions of changes, quality of life assessments (Pediatric Quality of Life Inventory [PedsQL™]), and health care resource use. Plasma concentrations of LCM and concomitant antiepileptic drugs (AEDs) will be obtained in order to develop a population PK model of LCM, to investigate the effect of LCM on the steady-state plasma concentrations of concomitant AEDs, and to investigate the correlation between LCM plasma concentrations and efficacy/or safety.

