5.2 Schedule of study assessments

[Table 5-1](#), [Table 5-2](#), and [Table 5-3](#) present the tabular schedules of study procedures.

Table 5-1 Schedule of study assessments (Baseline Period, Titration Period, Maintenance Period, Early Termination Visit, and Unscheduled Visits)

Assessments	Baseline Period (8 weeks)			Treatment Period (16 weeks)											ET	Unscheduled Visit ^c
	VI ^a	T1	V2	Titration Period (6 weeks)						Maintenance Period (10 weeks)						
Visit	VI ^a	T1	V2	T2	V3	T3	V4	T4	V5	V6	T5	V7	T6	V8 ^b	ET	Unscheduled Visit ^c
Week in study	-8	-4	0	1	2	3	4	5	6	8	10	12	14	16		
Informed consent	X															
Inclusion/exclusion criteria	X	X	X													
Medical history ^d	X															
Seizure history	X															
Concomitant medications	X	X	X	X	X	X	X	X	X	X	X	X	X	X	X	X
Concomitant AEDs	X	X	X	X	X	X	X	X	X	X	X	X	X	X	X	X
VNS assessment ^e	X		X		X		X		X	X		X		X	X	X
Physical examination (complete)	X		X											X	X	
Physical examination (brief)					X		X		X	X		X				
Tanner Stage ^f	X													X	X	
Vital signs (BP and pulse rate, including orthostatic assessments)	X		X		X		X		X	X		X		X	X	X
Body weight ^g	X		X ^g		X		X		X	X		X		X	X	X
Height	X		X											X	X	
Head circumference	X													X	X	
Neurological examination (complete)	X		X											X	X	
Neurological examination (brief)					X		X		X	X		X				
ECG (12-lead) ^h	X		X		X		X		X	X		X		X	X	

Table 5-1 Schedule of study assessments (Baseline Period, Titration Period, Maintenance Period, Early Termination Visit, and Unscheduled Visits)

Assessments	Baseline Period (8 weeks)			Treatment Period (16 weeks)											ET	Unscheduled Visit ^c
	VI ^a	T1	V2	Titration Period (6 weeks)						Maintenance Period (10 weeks)						
Visit	VI ^a	T1	V2	T2	V3	T3	V4	T4	V5	V6	T5	V7	T6	V8 ^b	ET	Unscheduled Visit ^c
Week in study	-8	-4	0	1	2	3	4	5	6	8	10	12	14	16		
Clinical chemistry/hematology	X		X				X		X			X		X	X	
Endocrinology			X											X	X	
Urinalysis ^d	X		X				X		X			X		X	X	
Serum pregnancy test ^e	X						X		X			X		X	X	
Urine pregnancy test ^f			X		X					X						
Concomitant AED plasma concentrations ^g	X								X					X	X	
LCM plasma concentration ^h	X								X					X	X	
C-SSRS ⁱ	X		X		X		X		X	X		X		X	X	X
Clinical Global Impression of Change														X	X	
Caregiver's Global Impression of Change														X	X	
Achenbach CBCL ^m			X						X					X	X	
BRIEF-P/BRIEF ⁿ			X											X	X	
PedsQL ^o			X											X	X	
Contact IXRS	X		X		X		X		X	X		X		X	X	
Randomization ^p			X													

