### **3.2.2 Study periods**

The study consists of the following six periods: Baseline Period, Titration Period, Maintenance Period, Transition Period, Taper Period, and Safety Follow-Up Period. Additionally for analysis purposes, the Treatment Period includes Titration and Maintenance Periods. Each period is defined in turn as follows for the classification by study period:

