### **8.1 Statistical analysis of the primary efficacy variable**

#### **8.1.1 Derivations of primary efficacy variable**

The primary efficacy variable is the change in partial-onset seizure frequency per 28 days from Baseline to the Maintenance Period. Seizure frequency per 28 days will be based on the number of days for which seizure information was provided during the specified time interval.

Seizure frequency per 28 days will be calculated as  $([\text{number of seizures over the specified time interval}] \text{ divided by } [\text{number of days in the interval}])$  multiplied by 28.

The partial-onset seizure frequency per 28 days will be calculated for both the Baseline Period and for the Maintenance Period, and the change from Baseline calculated.

If a seizure cluster is reported, the highest recorded daily seizure frequency during the Treatment Period for the seizure type associated with the report of a seizure cluster will be used as the imputed seizure frequency for the day on which the cluster occurred.

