#### **8.3.6 Hospital stays and emergency room visits**

Hospital stays and emergency room (ER) visits will be attributed to study periods as defined in section 3.2.2 based on admission date.

The number of hospital stays per subject during the Baseline Period and during the entire Treatment Period, separately, will be summarized by treatment group. The number of hospital stays will be summarized using the categories 0, 1, 2, 3, 4, and 5 or more. The number and percentage of subjects with specific reasons for duration of hospital stays will be summarized for the duration of the Baseline Period and for the duration of the entire Treatment Period, separately, by treatment group.

Duration of hospital stays will be categorized as 0 days, 1-5 days, 6-10 days, 11-15 days, and >15 days, and summarized for the duration of the Baseline Period and the duration of the entire Treatment Period, separately, by treatment group.

An event logged on the Hospitalization/ER Visit eCRF module where ER is marked as the initial entry point will be defined as an ER visit. An ER visit with a subject transfer to an inpatient general ward will also be counted as a hospitalization. However, all other instances of ER visits (where subject transfer is not to an inpatient general ward) will not be counted as hospitalizations. Descriptive statistics for the number of ER stays during the Baseline Period and for the duration of the entire Treatment Period, will be presented, separately, by treatment group. The number of ER visits will be summarized using the categories 0, 1, 2, and 3 or more. The number and percentage of subjects with specific reasons for duration of ER visits will be summarized for the duration of the Baseline Period and the duration of the entire Treatment Period, separately, by treatment group.

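### SAP 8.3.4 to 8.3.6 report health care resource use as raw counts over an 8-week Baseline and a Treatment Period of up to 16 weeks, with no allowance for time observed

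*SAP*

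**What the plan says.** Health care resource use is listed among the other efficacy variables, the tier below secondary (Protocol 4.1.3, SAP 2.2.1.3). Protocol 13.3.3 rules out statistical testing for that tier.

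- **Procedures (SAP 8.3.4).** The number per subject "will be summarized by treatment group for the Baseline Period and the entire Treatment Period, separately", in bands from 0 to 3 or more.
- **Consultations (SAP 8.3.5).** The number "per subject during the Baseline Period and during the entire Treatment Period will be summarized, separately", by arm, in bands from 0 to 5 or more.
- **Hospital stays and emergency room visits (SAP 8.3.6).** "The number of hospital stays per subject during the Baseline Period and during the entire Treatment Period" is tabulated by arm in bands, and emergency room visits are handled likewise. Hospital days are added up within a period and banded. A subject with no stay in a period is given 0 days.

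The periods differ in length. Protocol Section 1 sets out "an 8-week Baseline Period; a 6-week Titration Period" and then "a 10-week Maintenance Period at the dose of study medication achieved" on the last titration day. In SAP 3.2.2, "the Treatment Period includes Titration and Maintenance Periods". For a subject who discontinues, the same section ends the Treatment Period at the Early Termination Visit, or at the last visit or last known dose if there is no such visit.

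Neither document gives a rate, a person-time denominator or a restriction to completers for these tables. Seizures are handled differently in SAP 8.1.1: "Seizure frequency per 28 days will be based on the number of days for which seizure information was provided" in the interval.

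**The concern.** Procedures, consultations, stays and visits accrue with time, as seizures do. The SAP puts seizures on a 28-day scale and leaves health care use as raw counts, without giving a reason for the difference.

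Two misreadings follow. First, Baseline and Treatment summaries of the same quantity will be read together, and the longer window shows more use even if the rate has not moved. A reader cannot correct this by halving the Treatment figures, because category percentages do not scale in proportion to time. Second, within the Treatment Period a subject who leaves at Week 5 with no hospital stay is recorded as 0 days, exactly like a 16-week completer with none. Short observation then looks like low use.

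What is at stake is the reading of these descriptive tables, not a test or a claim of efficacy.

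**Working it through.** **Inputs from the documents.** Baseline 8 weeks, Titration 6 weeks and Maintenance 10 weeks (Protocol Section 1); Treatment Period 16 weeks (Protocol 5.2); planned dropout about 14% overall (Protocol 13.8); ceiling of 24% on the dropout rate in the sample size re-estimation (Protocol 13.7). Dropout by arm, time of exit and the rate of health care use are not given, so the values below are assumptions.

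**Period length.** 6 + 10 = 16 weeks, which matches the schedule. The ratio to Baseline is 16 / 8 = 2.0.

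**Mean counts, unchanged use.** For dropout fraction d and mean exit week t, mean weeks observed = (1 − d) × 16 + d × t. Dividing by 8 gives the apparent Treatment-to-Baseline ratio.

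- Completers only: 16 / 8 = 2.0.
- d = 14%, t = 3: 13.76 + 0.42 = 14.18 weeks, ratio 1.77.
- d = 14%, t = 6: 13.76 + 0.84 = 14.60 weeks, ratio 1.82.
- d = 14%, t = 8: 13.76 + 1.12 = 14.88 weeks, ratio 1.86.
- d = 14%, t = 12: 13.76 + 1.68 = 15.44 weeks, ratio 1.93.
- d = 24%, t = 3 to 12: 12.88 to 15.04 weeks, ratio 1.61 to 1.88.

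**Count categories, unchanged use, completers.** Assume Poisson counts with mean 0.5 per 8 weeks, hence 1.0 per 16 weeks.

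- At least one event: 1 − exp(−0.5) = 39% in Baseline and 1 − exp(−1.0) = 63% in Treatment, a 1.6-fold rise.
- Three or more events: 1.4% in Baseline and 8.0% in Treatment.

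**Between arms, equal true rates, dropout unrelated to use.** The apparent difference is the ratio of mean weeks observed, minus 1.

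| Assumed dropout | Mean exit week | Weeks observed | Apparent difference |
|---|---|---|---|
| 10% v 18% | 12 | 15.60 v 15.28 | −2.1% |
| 10% v 18% | 3 | 14.70 v 13.66 | −7.1% |
| 10% v 24% | 12 | 15.60 v 15.04 | −3.6% |
| 10% v 24% | 3 | 14.70 v 12.88 | −12.4% |
| 14% v 14% | same in both arms | equal | 0% |

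With 1:1 allocation, 10% v 18% averages the planned 14%. The pair 10% v 24% averages 17%, above plan, and should be read as a more extreme case.

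**Check of the rate.** Take the last unequal row at 0.5 / 8 = 0.0625 events per week. Expected events per subject are 14.70 × 0.0625 = 0.919 and 12.88 × 0.0625 = 0.805. Dividing each by its weeks observed and multiplying by 4 gives 0.25 per 28 days in both arms. Baseline gives 0.5 / 8 × 4 = 0.25 as well. Both spurious differences disappear under these assumptions.

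**The case against.** The strongest reply is that the plan never makes the comparison being criticised. The periods are summarised separately, and no change from Baseline, ratio or test is specified. Where the SAP wants change from Baseline it says so, as for PedsQL in 8.3.3. Period lengths are stated, exposure by arm is summarised in 10.1 and disposition by period in 5.1, and the underlying data are listed. Adverse event incidence in 10.2 is also given per subject without a time denominator, so this is a common descriptive convention. All of that is true, and it makes this a minor point. It does not remove the point: exposure summaries allow a rough correction of means but not of the category tables.

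Three stronger readings are tempting, and the documents do not support them.

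- **That unchanged use will simply appear to double.** This is exact only for completers' mean counts. It does not hold for all subjects together, nor for the percentage with any use. The provider-type percentages in 8.3.5 use the period's own consultations as denominator and do not scale with period length.
- **That the comparison between arms is biased towards the arm with more dropout.** This needs unequal dropout or timing, and similar use in dropouts and completers. The documents give no split by arm. The withdrawal criteria in Protocol 6.3 include intolerable adverse events and convulsive status epilepticus, so use may rise before exit and offset or reverse the effect. The 8 v 16 week mismatch itself does not touch a comparison of arms within one period.
- **That an efficacy conclusion is at risk.** These variables are untested, and no primary or secondary result depends on them.

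One practical objection also stands. SAP 8.3.6 assigns stays by admission date but runs duration to discharge, so hospital days can extend past the period. A rate needs a rule for that.

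**Conclusion.** The point holds as a minor weakness of presentation in descriptive tables. The period effect follows from the design alone: under an unchanged rate, mean use looks 2.0 times higher in completers and about 1.8 to 1.9 times higher at the planned dropout, given mean exit between Week 3 and Week 12. The shift in the category tables, 39% to 63% with any event, also rests on the assumed event rate and a Poisson model. The between-arm effect is conditional and modest, about 2% to 12% in the cases assumed. It is nil with balanced dropout and timing, and its direction is not assured if dropout is related to health care use.

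**What to change.** Add to SAP 8.3.4, 8.3.5 and 8.3.6, for each arm and period, a rate per 28 days: total events divided by total subject-days observed in that period, times 28. Take subject-days from the period dates already defined in SAP 3.2.2. For hospital days, count only days that fall within the period, and keep the existing rule that stays with partial dates are left out of duration. Keep the count categories as supporting displays.

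The cost is a few lines of SAP text and a little extra programming, with no new data collection. The rate does not remove bias if dropout is related to health care use, and a table footnote should say so.
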